Subjects may be re-screened, if deemed appropriate by the investigator and medical monitor. Unless otherwise stated, results of the following will be valid over the timeframes stated below (revised per Amendment 06):

- Tiers 1 to 3 Screening will be valid for 96 days from the date of assessment.
- Tier 4 MRIs will be valid for 90 days from the date of assessment.
- Tier 5 CSF results and amyloid PET scans will be valid for 90 days from the date of assessment, while historical amyloid PET scans will be valid for 12 months.

9.1.1.1.1 TIER 1

Subject demography and medical history will be obtained before completing the following cognitive/clinical assessments: MMSE, ISLT, CDR, and the modified Hachinski ischemic scale. (revised per Amendment 01) The Cogstate Brief Battery (CBB) will be administered in the 20 to 30 minutes between the ISLT total recall and delayed recall tests as a common distractor task. It is recommended that the MMSE and ISLT be completed, and eligibility on these assessments confirmed, before the CDR is administered. Subjects who are considered ineligible for the study based on these assessments should not continue with the rest of the Tier 1 assessments. For any given subject, every effort should be made to ensure that the CDR rater remains unchanged throughout the study. (revised per Amendment 04)

All subjects will be confirmed as meeting the diagnostic criteria for either MCI due to AD or the early stages of mild AD, and that they do not have other medical conditions that may interfere with study participation. The diagnosis and clinical disease staging will be verified via a central review process, and adjudicated if necessary (adjudication will only occur when there is a discrepancy between the diagnosis and clinical disease staging made by the site compared to that determined by the central review process; moreover, where adjudication is required, it will be undertaken by an independent assessor(s)). Confirmation of the diagnosis and clinical disease staging by central review will not be required in order for the subject to progress to Tier 2 of the Screening Visit, but will be required before the subject progresses to Tier 4. (revised per Amendment 04)

9.1.1.1.2 TIER 2

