9.1.2.1 Treatment Period

During Visit 2, the following assessments will be completed before the subject receives their first dose of study drug: MMSE, CDR, ADAS-cog14, FAQ, and NPI-10. (revised per Amendment 01) These assessments will provide baseline measurements for the study. For any given subject, every effort should be made to ensure that the CDR rater remains unchanged throughout the study. (revised per Amendment 04) Inclusion and exclusion criteria will be reviewed again together with concomitant medications and assessment of AEs. A single 12-lead ECG will be conducted. All ECG recordings will be evaluated by a central reader. (revised per Amendment 01) The C-SSRS will also be administered. A baseline routine physical examination with dermatologic review, vital signs measurements, clinical laboratory testing (including viral characterization), urinalysis using urine dipstick, and a urine pregnancy test (females of child-bearing potential only), will be performed. Additional blood samples will be taken for PD/exploratory biomarkers and immunologic assessments. (revised per Amendment 04) Some of the immunologic assessment blood sample will be used to prepare isolated PBMCs which will be stored for testing as required. (revised per Amendment 03) The results of some of the immunologic assessments will be provided to the DSMB for periodic review during the Core Study. (revised per Amendments 01 and 06) Whilst there is no prescribed order in which the assessments at each visit are to be performed, the subject component of the cognitive, functional and quality of life assessments are to be performed in the morning whenever possible, or consistently at the same time of the day and ideally should be completed before the more invasive procedures (eg, physical examination, ECG, blood draw).

Subjects will be randomized at Visit 2 (Day 1) to receive elenbecestat 50 mg per day or placebo administered orally QD in the morning with or without food. Subjects will be encouraged to stay at the site for observation for at least 30 minutes following their first dose of study drug. The duration of this observation period can be extended at the investigator's discretion, eg, if warranted by medical history or concomitant medication. (revised per Amendment 04) Double-blinding to study drug will be in effect throughout the Treatment Period.

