9.7.1.6.1 PRIMARY EFFICACY ANALYSIS

The primary analysis will be based on an intent to treat philosophy without regard to adherence to treatment. The primary analysis of the change from baseline in CDR-SB at 24 months will be performed to compare elenbecestat 50 mg per day versus placebo using a linear mixed effects model for repeated measures (MMRM) on the FAS. The MMRM model will include fixed effects of treatment group, visit, treatment group by visit interaction, baseline CDR-SB, baseline CDR-SB by visit interaction, and randomization stratification variables (ie, region [7 levels], clinical dementia [yes, no], and concurrent AD medication use at randomization [Visit 2] [yes, no]). *ApoE4* status may be included in the model if appropriate. (revised per Amendments 01, 02, and 06) An unstructured covariance matrix will be employed to model the covariance of within subject effect; if MMRM fails to converge then a covariance structure with fewer parameters from the following list will be employed according to the prespecified order in the list until the MMRM converges. The list of covariance structure will include Heterogeneous Toeplitz, Toeplitz, Heterogeneous Compound Symmetry, and Compound Symmetry. This primary analysis will include all observed post baseline data of the change from baseline in CDR-SB without imputation of missing values. The treatment effect for elenbecestat versus placebo will be compared at 24 months based on MMRM model. The LS means and difference in LS means between elenbecestat treatment group and placebo, and corresponding 95% CI will be presented.

The null hypothesis is that there is no difference in the mean change from baseline in CDR-SB at 24 months between elenbecestat 50 mg per day and placebo. The corresponding alternative hypothesis is that there is a difference in the mean change from baseline in CDR-SB at 24 months between elenbecestat 50 mg per day and placebo.

The primary analysis will be repeated to minimize the impact of change in concomitant AD medications where efficacy data after initiation of new AD medications and increase of current AD medications will be censored.

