9.7.2 Determination of Sample Size

The sample size for this study is estimated for comparison of elenbecestat versus placebo with respect to a pooled analysis of studies E2609-G000-301 and E2609-G000-302 for the change from baseline in CDR-SB at 24 months. Based on the available data from the placebo group in Study BAN2401-G000-201 (a recently completed study with a comparable subject population), the mean and the standard deviation of the change from baseline in CDR-SB at 24 months in the placebo group are assumed to be 1.46 and 2.05, respectively, instead of 1.75 and 2.05, which are originally assumed by the available data from ADNI (of amyloid positive, MMSE equal or greater than 24, late MCI [global CDR=0.5, CDR memory box \geq 0.5]). Therefore, assuming a 25% reduction in the mean change from baseline CDR-SB at 24 months for elenbecestat compared to placebo with common standard deviation of 2.05 and 30% dropout rate, a total sample size of 1900 subjects, 950 subjects in each treatment group, will be required to detect the treatment difference between elenbecestat and placebo using a 2-sample t test with 90% power at a significance level of 2 sided alpha =0.05.

The pooled data from 2 studies (E2609-G000-301 and E2609-G000-302) will comprise the total sample size of approximately 1900 subjects. At least 850 subjects will be randomized in each study. (revised per Amendment 06)

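### The primary MMRM is valid, but prespecifying the Screening CDR-SB and the baseline ADAS-cog14 and FAQ, all already scheduled before the first dose, would tighten it at little cost

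*Protocol*

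**What the plan says.** Section 9.7.1.6.1 lists the fixed effects of the primary MMRM as treatment, visit, and then "treatment group by visit interaction, baseline CDR-SB, baseline CDR-SB by visit interaction, and randomization stratification variables". The stratification variables are region (7 levels), clinical dementia (yes/no) and concurrent AD medication use (yes/no). For ApoE4 it adds that its "status may be included in the model if appropriate".

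Two other sections show what is known about each subject before treatment. Section 9.1.1.1.1 (Tier 1 of Screening) schedules the "cognitive/clinical assessments: MMSE, ISLT, CDR, and the modified Hachinski ischemic scale". Section 9.1.2.1 schedules, before the "first dose of study drug: MMSE, CDR, ADAS-cog14, FAQ, and NPI-10", and makes these the baseline values. Both sections ask sites to keep the same CDR rater for a subject throughout. Section 9.3.1 makes the Screening CDR an eligibility test: global score 0.5 and Memory Box at least 0.5.

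No section places the Screening CDR-SB, or the baseline ADAS-cog14, FAQ or MMSE, in the primary model. Under Section 9.7.1.2, the Full Analysis Set requires a baseline and a post-dose value of the primary measure only.

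**The concern.** The outcome scale is read twice before treatment, and the model uses one reading. If CDR-SB carries any measurement error, a second pre-treatment reading says more about where the subject truly started and can lower the residual variance at Month 24. A cognitive score and a functional score may add information on disease stage that a single CDR-SB and a yes/no dementia flag miss.

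These scores precede the first dose and treatment is randomised, so adjusting for them under a prespecified rule does not bias the comparison. At stake is the width of the confidence interval for the pooled primary comparison. The validity of the test is not in question.

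**Working it through.** **Inputs from Section 9.7.2.** The placebo mean change and SD: "the placebo group are assumed to be 1.46 and 2.05, respectively". The effect: "assuming a 25% reduction in the mean change from baseline CDR-SB at 24 months", so 0.25 × 1.46 = 0.365 points. The variability and loss: "with common standard deviation of 2.05 and 30% dropout rate". The test: "using a 2-sample t test with 90% power at a significance level of 2 sided alpha =0.05".

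**The plan's own figure.**
- Completers per arm = 2 × (1.960 + 1.2816)² × (2.05/0.365)² = 662.9, so 663.
- Allowing for dropout: 663/0.70 = 947.1, so 948 per arm and 1896 in total. The plan states 1900, so it reproduces.
- With 950 per arm, completers are 950 × 0.70 = 665. The standard error is 2.05 × √(2/665) = 0.1124. Power = Φ(0.365/0.1124 − 1.960) = 90.1%.

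No covariate gain enters this calculation.

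**Effect of removing a share r of the residual variance.** The residual SD becomes 2.05 × √(1 − r), with 665 completers per arm. The equivalent number of extra subjects is 1900/(1 − r) − 1900. The values of r are assumptions, since the protocol gives none.

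| r | Residual SD | Standard error | 95% CI half-width | Power | Worth in subjects |
|---|---|---|---|---|---|
| 0 | 2.050 | 0.1124 | 0.220 | 90.1% | – |
| 1% | 2.040 | 0.1119 | 0.219 | 90.4% | 19 |
| 4% | 2.009 | 0.1102 | 0.216 | 91.2% | 79 |
| 12% | 1.923 | 0.1055 | 0.207 | 93.3% | 259 |

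**Could r be in that range?** For the second CDR-SB alone, let the true baseline have variance s² and each reading an independent error of variance e². The uncertainty left about the true baseline is s²e²/(s² + e²) after one reading and s²e²/(2s² + e²) after two. The difference, divided by 2.05² = 4.2025, is the share removed. Assume a baseline SD of 1.0-1.6 and a reliability of 0.6-0.9.
- Low end (SD 1.0, reliability 0.9; s² = 0.90, e² = 0.10): 0.0900 − 0.0474 = 0.0426, or 1.0%.
- High end (SD 1.6, reliability 0.6; s² = 1.536, e² = 1.024): 0.6144 − 0.3840 = 0.2304, or 5.5%.

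A variant with baseline SD 1.0-1.3, which lets the true baseline correlate 0-0.4 with the true change, gives about 1-10%. No comparable derivation is possible for ADAS-cog14 and FAQ from what the protocol provides. The 12% end is therefore an allowance for all three scores together.

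**The case against.** The strongest reply is that nothing is wrong. The model is prespecified, includes baseline CDR-SB by visit and all the stratification factors, and meets its stated power without help. That stands, and it limits the point to an improvement.

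Several arguments also push the gain down, and they stand too:
- Dementia staging is already in the model and probably overlaps with what ADAS-cog14 and FAQ would add.
- The Screening CDR is the selection reading, so its range is restricted.
- The replicate calculation assumes independent errors. The same rater within a few months may repeat the same error, which shrinks the benefit.
- The 90.1% reference is the planning t test on completers. The MMRM already adjusts for baseline and uses partial follow-up, so its own starting power may differ and the increment may be smaller.
- Calling the Visit 2 score noisy has no figure behind it. Sections 9.2.1 and 9.2.3 describe CDR-SB as reliable.
- The change is not free. A subject without a baseline ADAS-cog14 or FAQ can be in the Full Analysis Set, and would drop out of the MMRM unless a rule covers the missing value.

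Two stronger readings are tempting. A reader might infer that the trial is underpowered or adjusts for nothing but one score; the reproduced sample size and the three strata rule that out. A reader might also infer from the ApoE4 clause that the primary model will be picked by its p-value. If ApoE4 explained 1-5% of variance and the better of two unblinded fits were reported, the two-sided error would be about 5.5-6.0%. But nothing in the protocol says the choice would be made that way or at that time, the 1-5% is an assumption, and such a choice is commonly settled in the SAP, which is not at hand. That error rate is not a demonstrated property of this plan.

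**Conclusion.** The point holds as a missed efficiency gain. The Visit 2 CDR-SB is the only quantitative severity covariate, and three further pre-treatment scores that may be prognostic go unused.

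On the planning basis of Section 9.7.2, the gain in power is about 0.3 to 3.2 points (90.1% to 90.4-93.3%), and the confidence interval narrows by about 0.5% to 6%. Both figures rest on an assumed 1-12% reduction in residual variance. Restricted range, shared rater error and overlap with dementia staging make the low end more likely.

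No benefit is shown for amyloid PET: nothing in the protocol suggests that these clinical scores predict change in SUVR. For ADCOMS the benefit is doubtful, because baseline ADCOMS, already in that model, contains all six CDR boxes, four ADAS-cog items and two MMSE items (Section 9.2.3, Table 1).

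**What to change.** - **Primary model.** In Section 9.7.1.6.1, add Screening CDR-SB, baseline ADAS-cog14 and baseline FAQ to the MMRM, each with its by-visit interaction.
- **Missing covariates.** State a treatment-blind rule, for example imputing the overall mean across both arms, so that no Full Analysis Set subject is lost.
- **Sensitivity analysis.** Use the same baseline scores in the multiple-imputation ANCOVA for CDR-SB. It concerns a single time point, so no visit terms are needed.
- **Other models.** Do not carry the scores automatically to the amyloid PET model. For ADCOMS, note the overlap with baseline ADCOMS before deciding.
- **ApoE4.** Record a firm yes or no before unblinding, in the protocol or the SAP. This is a clarification only.

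The cost is a sentence or two of text, a few parameters in a model with about 1900 subjects, and the missing-covariate rule. No new data are needed.

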The CDR will be conducted every 3 months during the Core Study; other cognitive and functional assessment instruments will be administered every 6 months. Every 3 months, the investigator is required to confirm the clinical staging of AD (ie, dementia or nondementia). This staging decision will be verified via a central review process and adjudicated if necessary (adjudication will only occur when there is a discrepancy between the clinical disease staging made by the site compared to that determined by the central review process; moreover, where adjudication is required, it will be undertaken by an independent assessor(s)). (revised per Amendment 01)

The health-related quality of life measures will be conducted every 6 months during the Core Study, along with the NPI-10.

MRI scans (including vMRI and fMRI) will be performed at 12 and 24 months during the Core Study or at the ED Visit/Follow-up Visit. If subjects have non-MRI compatible devices fitted during treatment, then a computed tomography scan may be utilized to assess safety, if deemed appropriate by the investigator. (revised per Amendment 06)

At every visit, AEs will be assessed, concomitant medications will be reviewed, physical examinations with dermatologic review by the study investigator will be performed, vital signs and respiratory rate will be measured, suicidality will be assessed, blood will be drawn for clinical chemistry, hematology, and for immunologic assessments. A urine sample will be provided for dipstick urinalysis. (revised per Amendment 01) Other assessments, including safety assessments (neurologic exams, ECGs, urine pregnancy tests for females of child-bearing potential), and blood draws for PK, PD, and assessment of immune status are performed at different intervals throughout the Treatment Period of the study.

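### The covariance fallback list tries equal-variance Toeplitz before heterogeneous compound symmetry, so if it is ever reached it can understate the Month 24 standard error unless empirical standard errors are used (minor)

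*Protocol*

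**What the plan says.** Section 9.7.1.6.1 of the Protocol makes the unstructured covariance the primary choice. The fallback is conditional: "if MMRM fails to converge then a covariance structure with fewer parameters from the following list will be employed according to the prespecified order". The order is then given: "The list of covariance structure will include Heterogeneous Toeplitz, Toeplitz, Heterogeneous Compound Symmetry, and Compound Symmetry".

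Three other statements bear on the point:

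- The test is at one visit: "The treatment effect for elenbecestat versus placebo will be compared at 24 months based on MMRM model".
- All visits feed the model: "This primary analysis will include all observed post baseline data of the change from baseline in CDR-SB without imputation of missing values".
- Section 9.1.2.1 sets the visit spacing: "The CDR will be conducted every 3 months during the Core Study". With Table 5 this gives eight on-treatment CDR assessments, at Months 3 to 24.

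The Protocol does not say how standard errors are computed in this model, and it names no degrees-of-freedom method. The only SD it gives for CDR-SB change is the Month 24 value in Section 9.7.2, where the placebo mean and SD "in the placebo group are assumed to be 1.46 and 2.05, respectively". It gives no SD for an earlier visit and no within-subject correlation.

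**The concern.** Change from baseline in a progressive disease usually spreads out over time. The Protocol's own slope analysis (Section 9.7.1.6.2) uses a random coefficient model, and if slopes differ between subjects the variance of change must grow with time. An equal-variance structure then assigns Month 24 roughly the average variance over visits, which is below its own. If the standard error comes from that fitted covariance, it is too small at exactly the visit where the hypothesis is tested.

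Heterogeneous compound symmetry, which keeps a separate variance at each visit, is tried only after Toeplitz. A prespecified order binds the sponsor at the moment it is needed, which is after unblinding, when a departure would look data-driven.

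**Working it through.** **1. Reproduce the planned sample size.** The effect is 25% of 1.46 = 0.365 and the SD is 2.05 (Section 9.7.2). Per arm, n = 2 × (1.960 + 1.282)² × 2.05² / 0.365² ≈ 663. Allowing for 30% dropout, 663 / 0.70 gives 948 per arm, or 1896 in total, against the stated 1900. The SD of 2.05 and 950 per arm are therefore used below.

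**2. Parameter counts for k = 8 visits.** Unstructured k(k+1)/2 = 36; heterogeneous Toeplitz 2k−1 = 15; Toeplitz k = 8; heterogeneous compound symmetry k+1 = 9; compound symmetry 2.

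**3. Rough check by hand.** Under equal variance the ratio of reported to true standard error at Month 24 is about √(mean variance over visits / Month 24 variance). Suppose the SD rises linearly from 1.0 (assumed) to 2.05 in steps of 0.15. The eight variances are 1.0000, 1.3225, 1.6900, 2.1025, 2.5600, 3.0625, 3.6100 and 4.2025, with mean 19.55 / 8 = 2.444. The ratio is √(2.444 / 4.2025) = 0.76. Type I error is 2 × [1 − Φ(1.96 × 0.76)], about 13.5%. Dropout gives the early visits more weight and lowers the ratio further.

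**4. Fuller large-sample calculation.** The model has eight visits with visit-specific means, 950 per arm, and 30% monotone dropout spread evenly over the visits and unrelated to outcome. Each structure was set to its best-fitting values. The model-based standard error of the Month 24 difference was then divided by its true (sandwich) standard error. Assumptions that are not in the Protocol are the Month 3 SD, its linear rise to 2.05, and the correlation: AR(1) with 0.9 or exchangeable with 0.6. Where two figures are shown, they are for AR(1) and exchangeable.

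| Assumed Month 3 SD | Toeplitz: SE ratio | Toeplitz: type I error | Heterogeneous CS: SE ratio | Heterogeneous CS: type I error |
|---|---|---|---|---|
| 2.05 (no growth) | 1.00 | 5.0% | 0.996 / 1.00 | 5.1% / 5.0% |
| 1.7 | 0.907 | 7.5% | 0.996 / 1.00 | 5.1% / 5.0% |
| 1.4 | 0.832 / 0.831 | 10.3% | 0.996 / 1.00 | 5.1% / 5.0% |
| 1.0 | 0.744 / 0.739 | 14.5% / 14.8% | 0.996 / 1.00 | 5.1% / 5.0% |
| 0.8 | 0.706 / 0.697 | 16.7% / 17.2% | 0.996 / 1.00 | 5.1% / 5.0% |

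In these cases heterogeneous Toeplitz has ratio 1.00 throughout.

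**5. Random-slope covariances** (Month 3 SD 0.75 to 1.12).

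| Structure | SE ratio | Type I error |
|---|---|---|
| Heterogeneous Toeplitz | 0.83–0.90 | 7.8–10.5% |
| Toeplitz | 0.70–0.76 | 13.9–17.2% |
| Heterogeneous CS | 0.94–0.95 | 6.2–6.5% |
| CS | 0.63–0.72 | 15.7–21.3% |

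Here the first structure on the list also understates the standard error, so reordering alone is not a full cure.

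**6. True precision.** The true Month 24 standard error hardly depends on the working structure: 0.102 to 0.106 under Toeplitz and 0.102 to 0.107 under heterogeneous compound symmetry. The harm lies in the reported standard error. A sandwich estimator reports the true one.

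**The case against.** The strongest reply is that the list will probably never be used. Unstructured comes first, and 36 covariance parameters with about 1900 subjects should be estimable. Toeplitz is reached only if heterogeneous Toeplitz fails too. That stands, and it is why the point is minor. The CDR-SB analysis restricted by baseline PET SUVR (Section 9.7.1.6.2) is a somewhat more plausible place for a double failure, because it keeps all eight visits on fewer subjects. It is, however, an other secondary analysis outside the sequential testing.

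Four stronger readings are tempting, and the Protocol does not support them.

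- A reader might infer that model-based errors are specified. They are not. The Protocol is silent on the estimator, which is commonly left to the SAP, and a sandwich estimator named there would already remove the bias in the standard error.
- A reader might infer that the primary test will miss its 5% level. That needs two convergence failures, growing variance and model-based errors together.
- A reader might see a contradiction in "a covariance structure with fewer parameters from the following list will be employed according to the prespecified order", because the count rises from 8 to 9 at the third entry. The natural meaning is fewer than unstructured, and 15, 8, 9 and 2 are all below 36.
- A reader might extend the point to amyloid PET. Scans are at 12 and 24 months only, so unstructured, heterogeneous Toeplitz and heterogeneous compound symmetry are the same three-parameter model. The order makes no difference to how soon a heterogeneous structure is tried.

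It is also fair to say that the sandwich estimator does most of the repair. Once it is used, the order matters little.

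**Conclusion.** The point holds as a minor, conditional weakness. As written, the order can lead to an equal-variance model for a single-visit contrast before a heterogeneous alternative has been tried. If that happens with model-based errors, and the Month 3 SD is between 1.7 and about 0.8, the Month 24 standard error is understated by about 9% to 30% and two-sided type I error is about 7.5% to 17%. Heterogeneous compound symmetry in the same place gives about 5.0% to 6.5%. If the SD does not grow, Toeplitz is unbiased.

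The size rests on assumed early SDs and correlations, because the Protocol supplies only the Month 24 SD. The calculation also treats dropout as unrelated to outcome, so it speaks to the standard error and not to bias in the estimate.

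**What to change.** Replace the list with this order: heterogeneous Toeplitz, heterogeneous compound symmetry, then Toeplitz and compound symmetry only as last resorts, stopping at the first that converges. Add that whenever the covariance is not unstructured, the standard error, confidence interval and p-value come from the empirical (sandwich) estimator. The second part is needed even with the new order, because heterogeneous Toeplitz can also understate the standard error under random slopes. If the SAP already names the sandwich estimator for structured fits, only the reordering remains.

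The cost is one sentence in the Protocol and the SAP, with no effect on data collection or sample size. The one technical drawback is that Kenward-Roger type degrees of freedom are not available with the sandwich estimator, which is negligible at this sample size.
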